5. STUDY POPULATION AND ELIGIBILITY

The study sites are Johns Hopkins Bayview and East Baltimore Campuses Adult Psychiatry Outpatient Program, Keypoint Inc., psychiatric day programs and outpatient clinics. PRPs have SMI patients attending regularly 3+ days/week and ample space for on-site group sessions and physical activity classes.

Approximately 4,800 persons with mental illness attend these programs.

We will enroll 220 adults with SMI who report nicotine dependence with a Fagerstrom Test for Nicotine Dependence (FTND)¹⁴⁷ score of ≥ 5 and are either interested in setting a quit date within 6 months (contemplation) or within the next 30 days (preparation). Based on Maryland Mental Hygiene data and Bayview reports, approximately 50-65% of the mental health consumers in our sites have nicotine dependence. Most consumers in the sites receive Medicaid and/or Medicare. Across the two sites, approximately 50% are women, 40% are African Americans, and mean age is 45 years. Approximately 40% have schizophrenia-related diagnoses; with bipolar disorder and depression each approximately 30%. An important goal of TRIUMPH will be generalizability across populations of SMI served in the community; thus eligibility criteria are broad with exclusion criteria mainly related to safety (Table 1).

Table 1. Eligibility Criteria

▪ Age 18 and older

▪ SMI—schizophrenia, schizoaffective disorder, bipolar disorder, or recurrent major depression meeting criteria for serious mental illness

▪ Daily cigarette smoking (or any smoked tobacco product e.g., mini-cigars, cigarillos) for at least the past 6 months (on days that smoked tobacco products were available)

▪ On stable psychotropic medication for mental illness for at least 30 days (i.e. antipsychotic medication for those with schizophrenia spectrum illness, mood stabilizer for those with bipolar disorder)

▪ Competent and willing to give informed consent

▪ Completion of baseline data collection

▪ Willing to participate in the smoking cessation intervention that includes combination of evidence-based behavioral (group and individual sessions) and pharmacotherapeutic smoking cessation aids

▪ Interested in quitting smoking within six months

Exclusion criteria

▪ Serious cardiovascular event within the past 6 months (e.g. myocardial infarction, stroke)

▪ Serious unstable medical condition which limits life expectancy

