7. DATA COLLECTION AND MEASUREMENTS

Outcomes and Measures are collected at baseline, 6, 12, 15 and 18 months at mental health programs. Table 2 shows these measures.

Primary Outcome: The primary outcome will be 7-day point prevalence smoking abstinence at 18 months, defined as self-report of 7 days of not smoking, confirmed by expired CO <8ppm with a Bedfont Smokerlyzer II.^{175,181,182} Biochemical verification with available urine cotinine (if not on NRT) and/or anabasine will be used as needed to confirm self-reported abstinence, particularly if the validity of CO is expected to be low (e.g. COPD or difficulty forming an adequate seal on the smokerlyzer); and if CO is greater than 8 as this could be from second hand smoke or smoked cannabis.¹⁴⁸⁻¹⁵⁰

7-day smoking abstinence at 6, 12 and 15 mo. are secondary outcomes.

Other Secondary outcomes focus on AHA metrics for health risk behaviors¹⁶⁵ and include: a) continuous abstinence with 1) % continually abstinent over 3mo. (based on self-reports of abstinence since last visit, using timeline follow-back)¹⁸³, and biochemical verification at 15 and 18 month visits), 2) total days abstinent in the study with the same method; b) Weight and BMI; c) Physical fitness with 6-minute walk;¹⁸⁴⁻¹⁸⁶ and d) Healthy diet.¹⁸⁷ We will assess 10-year probability of a CVD event with the global Framingham Risk Score (FRS) incorporating smoking, total and HDL-cholesterol, systolic blood pressure and diabetes mellitus.¹⁸⁸ Others include: health status (SF-12)¹⁸⁹; Quality of life (Euroqol);¹⁹⁰⁻¹⁹² psychiatric symptoms (BPRS);¹⁹³ ED use and hospitalizations.

We will also examine the difference of mean CO change over time between intervention arms, and, among

Protocol: Trial of Integrated Smoking Cessation, Exercise and Weight Management in SMI

continuing cigarette smokers, change of mean number of cigarettes smoked per day over time between intervention arms.

Measurement methods: Measures for all participants are detailed below, and will be conducted using standardized procedures, and following quality control procedures as in ACHIEVE and Drs. [name]' trials.^{51,61,121,125} The data collection team will be certified in and experienced with measures, and monitored by the study coordinator. All measures are collected at baseline, 6, and 18 months. At 12 months and 15 months we collect contact information, medications, smoking information, weight and event surveillance.

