Demographics, Medical History: We will collect demographics, contact information, medical history with checklist of conditions, Rose Angina Questionnaire, and assess alcohol use with the AUDIT (Alcohol Use Disorders Identification Test) and questions from the Semi-Structured Assessment for the Genetics of Alcoholism (SSAGA-II) and substance use with ASI-Lite.^{151,152}

Psychiatric diagnoses and medications are abstracted from charts. Participants confirm medications.

Tobacco smoking will be assessed with questions regarding self-reported smoking behavior since the last data collection visit and 6-item Fagerstrom Test of Nicotine Dependence (FTND).¹⁴⁷ At baseline we also assess smoking history including age of onset, cigarettes/day, pack-years, number of prior quit attempts, reasons for treatment failure or relapse, and self-efficacy around quitting. **We will measure** expired carbon monoxide (CO) and will also obtain urinary cotinine and anabasine as appropriate to confirm smoking status.^{148,150,153}

Weight will be measured to the nearest 0.1 lb by a high quality digital scale with participants wearing light indoor clothes without shoes. Weight will be measured in lbs. for ease of interpretation by participants and converted to kg for calculation of BMI, calculated as the Quetelet index.

Height to the nearest 0.1 cm will be measured at baseline using a wall-mounted stadiometer.

Physical fitness will be measured by the 6-minute walk test, a valid predictor of VO₂ max and responsive to increases in regular moderate physical activity.¹⁵⁴⁻¹⁵⁶

Blood pressure will be determined by the OMRON 907 XL, a validated device that records BP using an oscillometric technique.¹⁵⁷ On 3 visits, 1 week apart, 3 measurements (each separated by 30 seconds) will be obtained on the right arm of participants after they rest quietly in the seated position for at least 5 minutes.¹⁵⁸

Fasting blood measures will be collected, centrifuged, aliquoted and sent for processing. Total and HDL cholesterol, triglycerides, glucose, LDL cholesterol will be estimated by Friedwald equation unless direct measurement is needed.¹⁵⁹ An aliquot will be frozen for future investigation of putative CVD risk markers. Urinary protein will be measured.

Waist circumference will be measured with anthropometric tape, in a plane 1 cm above the navel.

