13. DATA ANALYSIS

Primary Outcome: The primary outcome will be 7-day point prevalence smoking abstinence at 18 months, defined as self-report of 7 days of not smoking, confirmed by expired CO <8ppm with a Bedfont Smokerlyzer II.^{148,153,218 182} Biochemical verification with available urine cotinine (if not on NRT) and/or anabasine will be used as needed to verify self-reported abstinence, particularly if the validity of CO is expected to be low (e.g. COPD or difficulty forming an adequate seal on the smokerlyzer); and if CO is greater than 8 as this could be from second hand smoke or smoked cannabis.¹⁴⁸⁻¹⁵⁰

7-day smoking abstinence at 6,12 and 15 mo. are secondary outcomes.

Other Secondary outcomes focus on AHA metrics for health risk behaviors²⁰² and include: a) continuous abstinence with 1) % continually abstinent over 3 mo. (based on self-reports of abstinence since last visit, using timeline follow-back²¹⁹, and biochemical verification at 15 and 18 month visits), 2) total days abstinent in the study with the same method, b) Weight and BMI; c) Physical fitness with 6-minute walk;¹⁵⁴⁻¹⁵⁶ and d) Healthy diet.¹⁶⁰ We will assess 10-year probability of a CVD event with the global Framingham Risk Score (FRS) incorporating smoking, total and HDL-cholesterol, systolic blood pressure and diabetes mellitus.²²⁰ Others include: health status (SF-12)¹⁶²; Quality of life (Euroqol);¹⁶³⁻¹⁶⁵ psychiatric symptoms (BPRS);¹⁷⁰ ED use and hospitalizations.

We will also examine the difference of mean CO change over time between intervention arms, and, among continuing cigarette smokers, change of mean number of cigarettes smoked per day over time between intervention arms.

For the primary outcome, we will also perform sensitivity analyses using expired CO<6ppm for abstinent confirmation, as this cutpoint has become more acceptable during the time the trial has been implemented.¹⁵⁰ The outcome using this alternative definition will be modeled in the same fashion.

Our recruitment goal is 220 participants will be recruited from 2 community mental health organizations, enrolled, and randomized in equal allocation to active intervention (Group B) and control (Group A), stratified

Protocol: Trial of Integrated Smoking Cessation, Exercise and Weight Management in SMI

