Although model (1) will support our principal analyses, there is an attractive, transition model alternative. A first-order, autoregressive transition model is a useful adjunct to (1). Note for each participant the outcome is a binary time series that can be analyzed via a series of linked, 2×2 tables (rows are values at visit $(j-1)$, columns at visit j , where visit 0 is baseline), with transitions modeled by logistic regression with treatment effects and, if desired, other covariates. This model could be used to characterize probability of successful abstinence at 12-months among those who were still smokers at 6-months, and at 18-months among those who were smokers at 12-months. Similarly we could estimate relapse rate at a given visit among quitters at the previous visit.

Missing data: Based on our experience, we anticipate less than 10% of follow-up data will be missing.¹²⁵ Prevention is far superior to statistical treatments; every effort will be made to collect data on all randomized. We will use two approaches to missing data. First, in smoking cessation trials, conventionally, those missing smoking data are assumed to be smoking, and we will use this method to be comparable to the field.

^{203,204,222,223} Second, we will perform analyses on the assumption that data is missing at random (MAR). The underlying missing data process determines the biasing effects of missing data and structures valid analytic strategies.²²⁴ If the probability of a potential observation being missing depends on what has, but not on what has not been observed, termed MAR, then estimates based on an appropriate analytic model (both the mean and error structure) for the observed data will not be biased. A valid model for the observed data allows the missing data process to be ignored. If missing is informative, meaning that the probability of an observation being missing depends on the value of that observation after accounting for all the observed data, then bias cannot be avoided by modeling the observed data alone, and the impact should be evaluated using sensitivity analysis. Given that MAR is not a testable hypothesis, we will perform sensitivity analyses to evaluate the robustness of MAR results with multiple imputation using a model derived from our analytical model under MAR, maintaining the covariance structure and modifying the imputation mean according to informative missing data scenarios.

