Secondary Analyses (Secondary Aims 1-2): The odds ratio of maintaining continuous abstinence over 15 to 18 months months will be modeled using logistic regression. To evaluate between group difference in change for secondary continuous outcomes such as continuous smoking abstinence (number of days abstinent), weight, 6-minute walk test, global FRS, and psychiatric symptoms (BPRS), we will use linear mixed models employing visit by intervention interaction terms in the mean model and unstructured correlation in the covariance model to estimate intervention effects over time. Outcomes will be log-transformed as appropriate. Emergency department visits and hospitalizations over the three 6-month periods (0-6, 6-12, 12-18 months) will be modeled using mixed effect Poisson regression. All these analyses will be conducted under intention to treat principles. Covariates such as study site and set quit date indicators and other variables associated with

Protocol: Trial of Integrated Smoking Cessation, Exercise and Weight Management in SMI

presence of missing data will be included in the mean model as appropriate.

We will also explore the difference of mean CO change over time between intervention arms, and, among continuing cigarette smokers, change of mean number of cigarettes smoked per day over time between intervention arms using mixed effects regression modeling approach in a similar fashion. For the first exploratory analysis, we will use all patients in the analysis. In the second analysis, we will determine if patients who continue to smoke, smoke less. In this analysis, we will include only patients who are not abstinent. We will use the pattern mixture approach by examining patients in separate groups according to their pattern of missing data to better understand the probability of missing based on patterns of the observed data to inform proper modeling and sensitivity analyses addressing potential informative missing mechanism.

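### The exploratory between-arm comparison of cigarettes per day keeps only non-abstinent participants, a set formed after randomisation, and the plan's caution about such subgroups does not reach it

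*Combined protocol and SAP*

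**What the plan says.** Section 13, Secondary Analyses, describes two exploratory mixed-model analyses of smoking reduction. The first, of expired CO, is unrestricted: "For the first exploratory analysis, we will use all patients in the analysis". The second compares, "among continuing cigarette smokers, change of mean number of cigarettes smoked per day over time between intervention arms". Its purpose is stated: "In the second analysis, we will determine if patients who continue to smoke, smoke less". So is its analysis set: "In this analysis, we will include only patients who are not abstinent". Section 7 lists the same comparison among the outcomes.

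Two nearby passages might be thought to cover the restriction:

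- The sentence that follows it proposes a pattern-mixture approach, which groups patients by their pattern of missing data.
- Under Exploratory Analyses (Aim 3), the plan recognises that subgroups formed after randomisation lose its protection against confounding. It proposes propensity-score stratification and cautious interpretation. That text concerns outcomes in the active arm and potential mediators such as attendance, pharmacotherapy use and texting.

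The analysis is labelled exploratory here and in the protocol notes for version 1.2.

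**The concern.** Abstinence is the primary outcome and the thing the intervention is designed to change. If the intervention works as projected, more people leave the active arm's analysis set by quitting than leave the control arm's. A difference in cigarettes per day between those who remain then mixes two things: any effect of the intervention on people who go on smoking, and the difference between arms in who was removed. A reader who sees a between-arm mixed model beside the randomised analyses, with no warning attached, could take it as a randomised effect.

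Neither nearby passage closes the gap. A confirmed quitter is observed and then excluded, not missing, so the pattern-mixture step does not address the selection. The Aim 3 caution mentions neither abstinence status, nor cigarettes per day, nor a between-arm contrast. The companion CO analysis does keep all patients, but its outcome is CO.

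The stake is limited to how this one exploratory comparison is interpreted.

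**Working it through.** The plan gives no figure for this analysis, so there is none to reproduce. The check sizes the selection and then the bias it could produce.

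**Inputs from the documents.** 220 participants allocated equally, so 110 per arm; abstinence of 17.5-21.5% (active) and 3-5% (control); people lost to follow-up counted as smokers (all Section 13). On missing data, Section 13 states "we anticipate less than 10% of follow-up data will be missing". Section 16 gives a mean of 27 cigarettes per day at enrolment in prior studies. The documents give no SD of change and no relation between consumption and quitting.

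**1. Who remains.** Retained = 110 x (1 - abstinence rate).

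- Active: 110 x 0.825 = 90.75; 110 x 0.785 = 86.35.
- Control: 110 x 0.97 = 106.7; 110 x 0.95 = 104.5.

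The plan's rates count people lost to follow-up as smokers, so fewer would have a cigarette count. With 10% (11 per arm) missing, the counts are 79.75 to 75.35 active and 95.7 to 93.5 control.

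**2. Worst-case bound.** Assume that change is normally distributed, that the intervention has no effect on consumption while smoking, and that nobody quits only under control. The extra share removed from the active arm is q = (pA - pC)/(1 - pC).

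- 17.5% vs 5%: q = 0.125/0.95 = 0.132.
- 21.5% vs 3%: q = 0.185/0.97 = 0.191.

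If all of these people lay at one end of the distribution, the mean would shift by phi(z)/(1 - q), where z is the (1 - q) normal quantile. That gives 0.246 and 0.336 SD. The SE of a difference, in SD units, is sqrt(1/90.75 + 1/104.5) = 0.143 and sqrt(1/86.35 + 1/106.7) = 0.145. The ratios are 1.71 and 2.32 SE, in either direction. With 10% missing, the bound is 0.270-0.369 SD (1.77-2.39 SE).

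**3. A model like the one planned.** The simulation used baseline plus four follow-ups, an unstructured covariance fitted by maximum likelihood, and abstinent visits dropped. Assumed inputs were a person-level logit SD of 1.5 for quitting and a correlation of 0.6 or 0.85 between visits. The true effect on consumption while smoking was zero.

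| Quitting depends on | Bias, cigarettes per day |
|---|---|
| nothing related to consumption | about 0 |
| baseline consumption only | about 0 |
| current consumption | -1.2 to +1.2, at most about 0.85 SE |

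Here, about 0 means within 0.11, with a Monte Carlo SE of 0.03-0.07.

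**4. A simpler case.** This has one follow-up, with abstinent patients excluded. It uses 216 combinations of assumed consumption distributions, correlations and quitting slopes with the plan's abstinence rates. The bias ran from -0.93 to +0.95 per day unadjusted (at most 0.64 SE) and from -1.56 to +1.48 adjusted for baseline (at most 1.24 SE). These are extremes. The median adjusted bias was 0.03 SE, about 2% of combinations exceeded 1 SE, and none exceeded about 0.05 SE where quitting depended on baseline consumption. This is not the planned longitudinal model, so step 3 is the better guide.

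**The case against.** The strongest reply is that the restriction is the question. The plan asks whether people who go on smoking smoke less, and no all-randomised analysis answers that. If quitting is unrelated to consumption, quitting alone would produce about (0.19 - 0.05) x 27 = 3.8 cigarettes per day in an all-randomised analysis, so much of the added estimate would restate the primary outcome. The analysis is already labelled exploratory, an all-patient CO comparison stands beside it, and the plan shows elsewhere that its authors understand post-randomisation subgroups. In the closest model, the bias is near zero in two of three scenarios.

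Most of this stands. It is why the restricted analysis should stay and why the point is minor. What remains is that the exploratory label signals low evidential weight without saying that randomisation no longer protects the contrast, and the written caution does not extend to it.

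Three stronger readings are tempting and are not supported:

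- A reader might infer that Section 7 and the outcome list in Section 13 define a different population from the Secondary Analyses paragraph. They do not conflict: Section 7 has "continuing cigarette smokers, change of mean number of cigarettes smoked per day over time between intervention arms", and the Secondary Analyses paragraph uses both that term and the non-abstinent one. What is open is narrower. Eligibility covers "Daily cigarette smoking (or any smoked tobacco product e.g., mini-cigars, cigarillos) for at least the past 6 months", so a non-abstinent participant need not be a cigarette smoker.
- A reader might infer that the restriction breaks the plan's intention-to-treat commitment. That sentence comes before the exploratory paragraph and need not govern it.
- A reader might infer a bias of known direction, or treat the bound in step 2 as expected. The documents give no relation between consumption and quitting, and the bound requires every extra quitter to lie at one extreme.

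**Conclusion.** The point holds as a minor one about interpretation. The comparison is made in a set selected after randomisation on the outcome that the intervention targets, with projected losses of about 19-24 active against 3-6 control participants, and no caution in the plan covers it.

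The size and direction of any bias are not known in advance. It is zero if quitting is unrelated to consumption. Under assumed inputs in a four-visit mixed model, it is about zero if quitting depends only on baseline consumption, and up to about 0.85 SE either way if it depends on current consumption. The 1.7-2.3 SE bound is a limit, not an estimate. The retained counts rest on the plan's projected abstinence rates. The simulated values also rest on assumed correlations and quitting relations, and other assumptions give other values. The primary and secondary conclusions are unaffected.

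**What to change.** 1. Keep the continuing-smoker analysis, since it answers the stated question. Report it by arm (number, baseline consumption, change) as a non-randomised exploratory summary, and extend the Aim 3 caution to it.
2. Beside it, add a between-arm analysis of cigarettes per day in all randomised participants. Enter biochemically confirmed abstinent visits as 0 and use a model suited to zeros, such as a log-link GEE with robust standard errors. Treat missing counts as missing, by a method valid under MAR. If GEE is used, that means multiple imputation or weighting, because an unweighted GEE is not generally valid under MAR. Carry over the plan's informative-missingness sensitivity analyses.
3. While editing, state whether non-abstinence is judged per visit or per patient, how users of other smoked tobacco are counted, and how to treat someone who reports no smoking but fails verification. That person is not abstinent, yet has a reported count of zero.

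The cost is a few sentences and one extra model. No new data are needed: "Tobacco smoking will be assessed with questions regarding self-reported smoking behavior since the last data collection visit", and Table 2 schedules tobacco measures at every visit. The downside is that the added estimate combines quitting with reduction and does not by itself show whether continuing smokers smoke less. The two results should therefore be read together.
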